5.1 Inclusion Criteria

- Age Requirement: Female Chinese college basketball players aged between 18 and 24.
- Shoulder Injury Requirement: Diagnosed with shoulder joint injuries (e.g., rotator cuff injuries, tendon damage, shoulder dislocation) with no previous surgical treatment.
- Sports Background: Participating in basketball training with at least three training sessions per week and a certain level of sports experience.
- Informed Consent: Willing to participate in the study and sign the informed consent form, with the ability to understand and cooperate with the research-related questionnaires and treatment plans.
- Physical Health: No severe cardiovascular, neurological, or musculoskeletal disorders that impact physical performance.

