6.2 Traditional Rehabilitation Group

Participants will undergo conventional rehabilitation exercises, such as resistance training and mobility drills, guided by a physical therapist.

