6.3 Control Group

Participants will not receive any formal rehabilitation intervention but will continue with their usual basketball training.

7. Discontinuation and Withdrawal

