7.1 Discontinuation of Intervention

If a participant experiences excessive discomfort or injury during the rehabilitation process, they will be allowed to withdraw from the study. The study protocol allows for flexible adjustments to ensure participants' safety.

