10.3 Participant Protection

The study ensures participant protection through:

Minimizing Risk: Interventions are non-invasive, with regular monitoring for any adverse effects.

Confidentiality: All data will be anonymized and securely stored.

Ethical Oversight: The study adheres to the Declaration of Helsinki and national ethical guidelines.

11. Participant Timeline

Stage	Timeline	Description
Recruitment	July 15 • July 18, 2024	Participants are recruited, screened, and provided with the informed consent form.
Screening and Baseline Assessment	July 19 • July 21, 2024	Initial assessments of shoulder ROM and pain levels (VAS), confirmation of eligibility.
Pre-Intervention Evaluation	July 22, 2024	Final baseline evaluation and randomization of participants into intervention groups.
Intervention Period	July 22 • September 9, 2024	Participants undergo 9 weeks of VR-assisted or traditional rehabilitation, or no intervention (control group).
Mid-Point Evaluation	August 15, 2024	Mid-intervention check-in to assess progress, adherence, and potential adjustments.
Post-Intervention Evaluation	September 10 • September 13, 2024	Final assessments of shoulder ROM and pain levels, along with participant feedback on engagement.
Follow-Up	September 13, 2024	Final data collection and study conclusion.

12. Data Management Plan

All participant data, including demographic information, assessment results (range of motion and pain scores), and session attendance, will be collected and recorded on standardized data collection forms. Each participant will be assigned a unique study ID number to ensure confidentiality.

Data Handling Procedures:

- Paper-based data will be digitized and stored in a password-protected, encrypted database on a secure personal computer accessible only to the research team.
- Electronic data will be backed up weekly on an encrypted external hard drive.
- All personal identifiers will be removed from the dataset before analysis.
- Only de-identified data will be shared in publications or public databases.

Data Integrity and Quality Control:

- Double data entry will be employed to reduce transcription errors.
- Data will be periodically reviewed for completeness and consistency.
- Any missing data will be handled using appropriate statistical imputation methods or sensitivity analyses, as described in the statistical plan.

All procedures will comply with ethical guidelines for the protection of human participants and data privacy.

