13. Safety Monitoring

Although the interventions in this study are non-invasive and carry minimal risk, appropriate safety monitoring procedures will be implemented to ensure participant well-being.

Key Safety Procedures:

- All participants will be screened before enrollment to ensure eligibility and minimize risk.
- A licensed physical therapist will supervise each VR rehabilitation session to monitor physical exertion and movement quality.

- Participants will be instructed to report any signs of discomfort, dizziness, pain, or fatigue immediately during or after each session.

Adverse Event Handling:

- Any adverse events (AEs), whether mild or serious, will be documented and evaluated by the investigator.
- Participants experiencing significant AEs will be referred for medical evaluation and may be withdrawn from the study if necessary.
- A safety log will be maintained for transparency and accountability.

Regular check-ins and post-session debriefings will be conducted to ensure both physical and psychological safety throughout the study.

14. Limitations of the Study

While this study is designed with scientific rigor and careful planning, several limitations must be acknowledged:

1. Sample Size: The relatively small sample size ($n = 40$) may limit the statistical power and generalizability of the results to larger populations or different athletic groups.
2. Short Intervention Duration: The 4-week intervention period, although adequate for observing changes in ROM and pain, may not capture long-term rehabilitation outcomes or recurrence rates.
3. Single-Center Study: Conducting the study at a single university or region may introduce selection bias and limit external validity.
4. Self-Reported Pain Measures: The use of self-reported Visual Analogue Scale (VAS) scores for pain may be influenced by individual perceptions and psychological factors.
5. Participant Adherence: Although engagement is expected to be high in VR-assisted groups, individual differences in motivation, fatigue, or scheduling conflicts may affect adherence to the protocol.

Future studies with larger sample sizes, multicenter designs, longer follow-up periods, and objective pain assessments (e.g., biomarkers, neuroimaging) are recommended to validate and extend the findings.

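### Section 13 asks about harms mainly around sessions, and no occasion for asking about adverse events is common to all three arms, so ascertainment is likely to be less intensive in controls

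*Protocol*

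**What the plan says.** **Prompts that depend on sessions.** Section 13 (Safety Monitoring) gives three concrete ways of noticing harm once the study is running. One is a standing instruction: "Participants will be instructed to report any signs of discomfort, dizziness, pain, or fatigue immediately during or after each session". The second is observation: "A licensed physical therapist will supervise each VR rehabilitation session to monitor physical exertion and movement quality". The third is a debriefing after each session. Section 7.1 is worded in a similar way: "If a participant experiences excessive discomfort or injury during the rehabilitation process", the participant may withdraw. Section 10.3 attaches its monitoring promise to the interventions: "Interventions are non-invasive, with regular monitoring for any adverse effects".

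**The control arm.** Section 6.3 says of controls: "Participants will not receive any formal rehabilitation intervention but will continue with their usual basketball training". Like everyone else, they must meet Section 5.1: "Diagnosed with shoulder joint injuries (e.g., rotator cuff injuries, tendon damage, shoulder dislocation) with no previous surgical treatment", with at least three basketball training sessions a week.

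**Provisions not limited by arm.** Section 13 also has every adverse event documented and evaluated by the investigator, has significant events referred for medical evaluation with possible withdrawal, keeps a safety log, and promises regular check-ins during the study. Section 7.2 lets anyone withdraw at any time. The section on recruitment and retention (the second one numbered 5.3) promises regular follow-ups. Section 11 lists a mid-point evaluation on August 15.

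**The concern.** Recording an event and finding it are different steps. The clauses that cover all arms mostly say what happens once an event is known. The prompts that would bring an event to light are mostly placed at sessions that one arm does not have.

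Two things are at stake. The first is participant safety: controls have injured shoulders and continue a sport that loads them, so worsening could come to the team's attention later than it would in a rehabilitation arm. The second is interpretation: an arm that is asked more often tends to report more. A safety log filled this way could show more events under VR partly because VR participants are prompted and watched at each session. Events never asked about cannot be recovered in the analysis.

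**Working it through.** The protocol gives no figure to reproduce on this point, so the check is mainly a comparison of its provisions by arm.

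| Provision (protocol section) | VR | Traditional | Control |
|---|---|---|---|
| Symptom report at each session (13) | yes | yes | none, unless *session* includes basketball training |
| Safety supervision of sessions (13) | yes, named | not named; exercises are "guided by a physical therapist" (6.2), with no stated safety role | none |
| Debriefing after sessions (13) | yes | yes | none on the same reading |
| Wording of 7.1 | reached | reached | not reached by its wording |
| Documentation, referral, possible withdrawal, safety log (13) | yes | yes | yes |
| Withdrawal at any time (7.2) | yes | yes | yes |
| Regular check-ins (13), regular follow-ups (5.3) | no arm limit; frequency and content not stated | same | same |
| Mid-point evaluation, August 15 (11) | no arm limit; purpose is progress, adherence and adjustments, harms not named | same | same |

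**What *session* means.** Section 5.1 uses the word for basketball training, so the reporting instruction could be read to include it. In Section 13, however, the instruction comes directly after the bullet on VR rehabilitation sessions, lists dizziness among the symptoms, and sits alongside post-session debriefings by the study. Rehabilitation sessions are the likelier meaning, but the text does not say so.

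**Share affected.** Section 9.2 plans 15 per group, so 15/45 = 33% of participants have no session-based prompt. Section 14 gives a total of 40 instead. With near-equal groups that would be 13 or 14 controls (13/40 = 32.5%, 14/40 = 35%), so the share stays at about one third.

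**Dated contacts.** In Section 11, July 22 to August 15 is 24 days, and August 15 to the post-intervention window of September 10 to 13 is 26 to 29 days. Section 1.3 starts the intervention on July 15 and ends it on September 13, which would make the two intervals 31 and 29 days. These are intervals between dated contacts only. Undated check-ins or follow-ups may fall inside them, so they do not measure time without contact.

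**What cannot be computed.** No session frequency is given for either rehabilitation arm, and no frequency for the check-ins. The ratio of prompts between arms therefore has no value that can be derived from the protocol.

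**The case against.** The strongest reply is that controls are covered already, and much of it stands. The adverse-event handling rules in Section 13 have no arm or session limit, and 7.2 lets any participant leave at any time. A reader might infer that adverse-event reporting as a whole is tied to rehabilitation, or that controls fall outside every stopping provision. The text supports neither.

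Section 7.1 is headed as discontinuation of intervention, and controls have no intervention to discontinue. Its wording is natural in that place and does not contradict 6.3. What remains is that 7.1, 7.2 and Section 13 describe withdrawal after harm in three different scopes and should be made to agree.

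A reader might also take the 24- and 26-day intervals as periods in which a control is unobserved. That does not follow, for the reason given with the dates: undated contacts are promised, and the protocol's two timelines conflict. Pain and range of motion are also measured in every arm at the end, so the fair worry is late detection rather than none.

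Finally, no objective, outcome, hypothesis or analysis in the protocol compares safety between arms. It would go too far to say that the trial's safety conclusion is invalid, since none is planned, or that the log will show excess harm with VR. Unequal collection is an inference from the missing common prompt; the protocol does not state it.

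The reply does not supply an occasion on which all three arms are asked about harms in the same way. The check-ins could serve, but the protocol does not say that they do.

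**Conclusion.** The point holds in limited form. The active prompts for harms are worded around sessions, most naturally rehabilitation sessions, and no occasion for asking about adverse events is common to the three arms. Ascertainment is likely to be less intensive in controls, about one third of participants. It may also differ between VR and traditional rehabilitation, because Section 13 names supervision for VR alone. Worsening in a control could be noticed late, and event counts by arm would not be directly comparable.

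This rests on two assumptions: that *session* means a rehabilitation session, and that the unspecified check-ins and follow-ups do not already include a uniform question about harms. If either fails, the imbalance shrinks, but the protocol would still need to say so. The size of any distortion is unknown. The primary range-of-motion analysis is not affected. This is a cheap improvement to study conduct.

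**What to change.** In Section 13:

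- Turn the promised check-ins into one identical adverse-event question, asked by the existing team at the same fixed interval in all three arms. It should cover events during basketball training as well as during rehabilitation.
- Record the answers in the existing safety log, and mark events that came to light at a session separately.
- Base any between-arm statement about harms only on events found through the common question.
- Define *session*.

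Reconcile the wording of 7.1 with 7.2 and Section 13 so that their scopes agree. The content of any clinical rule, and the action taken on an event, stay with the investigator.

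The cost is a short amendment and a brief routine query. The small downside is slightly more contact with controls.
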